The recruitment plan will aim for an equal number of subjects in the DRC and SAU groups, and participants will be block randomized across potential moderator variables including medication and grade level. In the Goal 2 study, for which these variables were unselected, 52% of the final sample was prescribed medication and 66% were in grades K-3 and 34% were in grades 4-6. Thus, it appears that the plan to have an equal number of subjects in each block is feasible with careful attention to recruiting participants in the older grades in the present application. Block randomization based on child psychoactive medication status will promote equal distribution of participants across this variable. The medication variable will be defined as “no medication” if the child is not prescribed psychoactive medication immediately prior to randomization and as “taking medication” if the child is prescribed psychoactive medication and it is being actively administered at the time of randomization. In sum, an equal number of participants (N=72/year) will be enrolled in four blocks each year (i.e., No medication/Primary grade; No medication/Intermediate grade; Taking medication/Primary grade; Taking medication/Intermediate grade). Random assignment will be conducted following the completion of all baseline measures by a blinded member of the study team ([name]). Following randomization, a form letter will be generated that informs the study staff and participating family of group

assignment. Consultants will then be randomly assigned to the case with an equal number of DRC and SAU cases assigned to each consultant.

For those students who are medicated with stimulant medication, we will ask parents to obtain permission from the child's doctor to withhold medication for the assessment days in January and May so as to collect information on the child's behavior when unmedicated.

Intervention Groups

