DRC group. Students assigned to the DRC group will have a consultant assigned to the student for the duration of the school year. During the month of January, the consultant will work with the child's primary special education teacher (or regular education teacher if the child spends the majority of his or her day mainstreamed) to establish a DRC over the course of three consultation visits. The How to Establish a Daily Report Card manual contains a standard DRC instruction packet that is provided to teachers to explain the rationale of the DRC, procedures for creating, modifying, and evaluating the DRC, procedures for parents to create home-based rewards for DRC performance, and information on trouble-shooting. In addition, the packet contains consumable hand-outs that may be used to facilitate the meeting of these goals. This packet will be used as a starting point in all DRC consultations, and it was successfully modified, used, and evaluated in our Goal 2 project.

The first visit will be spent reviewing the IEP with the child's teacher(s) and conducting an interview to determine the behavioral procedures the teacher currently uses to manage child behavior as well as identify potential target behaviors not currently included on the IEP. At this meeting, target behaviors will be identified, operationally defined, and integrated into a DRC. The teacher will be asked to implement the intervention during the week between the first and second visit. At the second consultant visit, target behaviors will be refined, and using the data collected by the teacher, criteria for each target behavior will be modified (e.g., a child who averaged 10 verbally intrusive behaviors per class would have a target behavior changed to "Has 8 or fewer verbally intrusive behaviors"). The third consultant visit will be conducted to fine-tune and trouble-shoot the DRC and inform the teacher of the home rewards established by the parents. During this visit, the consultant will also establish a weekly time for the teacher to fax/call in a summary of DRC results for the week. DRCs will be implemented across settings and classes; however, a single teacher will be identified for assessment completion, observations will be conducted in that teacher's class, and this individual will be required to attend all consultant meetings.

The DRC will include direct accounting for IEP goals as well as other behavior problems common to a child with ADHD, and it is necessarily

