After the three initial meetings with the child’s teacher, consultants will meet monthly with the teacher (and parent if available) to provide feedback on the child’s behavior during the month using a graphical representation of the child’s DRC performance. This information will be used for data-driven decision making, a procedure shown to be better than teacher impressions/judgments when intervention planning/monitoring (Fuchs et al., 2000) and potentially critical for IEP monitoring. DRC goals will be adjusted as needed. It is expected that these monthly meetings will serve the purpose of ensuring IEP goals and objectives are consistently addressed on the DRC throughout the year.

SAU group. Consultants will conduct an initial meeting with each teacher of children in the SAU group to describe study procedures, establish regular classroom observation times, and obtain an updated copy of the child's IEP. All procedures will be implemented in the IEP as planned (e.g., counseling, school interventions). This condition is conceptualized as a school as usual control and serves as the counter-factual condition for the study.

To account for consultant contact with the teacher, consultants will meet with the teachers in the SAU group once per month. During these meetings they will collect information on how the child is functioning, and obtain information on any new, discontinued, or modified interventions (reward and/or punishment). The consultant will work with the teacher to construct a list of goals and criteria for meeting goals consistent with the approach used in the DRC group. This list of goals will not be used to develop DRCs or other classroom interventions but will be used by the observer to record teacher feedback to the child related to targeted behaviors. Our goal 2 study had teachers fill out an Individualized Target Behavior Checklist (ITBC; [name], [name], & Massetti, 2005), which was constructed in the same manner as a DRC, but feedback on target behaviors was not provided to the child or parents and contingencies were not provided at school or home. Our Goal 2 study suggested that the ITBC had no appreciable effect on behavior ([name] et al., 2009, 2010) replicated by other studies ([name], [name], et al., 2016).

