Impairment Rating Scale (Evans, Allen, Moore, & Strauss, 2005; [name] et al., 2006). The IRS is a rating scale that asks teachers to rate the severity of the child's problems and need for treatment and/or special services in important functional domains (i.e., relationship with peers, relationship with the teacher(s), academic progress, classroom functioning, self-esteem, overall need). There are six items on the scale, and scores on the measure range from zero (Not a problem/Definitely does not need treatment or special services) to six (Extreme problem/Definitely needs treatment or special services). Test-retest reliability estimates range from .60-.89 over a period of six months, and .54 to .76 over one-year. Ratings on the IRS predict mental health or school services, and there is evidence of convergent and discriminant validity on the measure ([name] et al., 2006). The average score for each of the individual domains rated will be used in the analysis; scores range from 0.0-6.0.

Rating of IEP Goals ([name], et al., 2010; Guy, 1976; [name] & Hoza, 1996; [name] et al., 2000). At each of the classroom observations, observers will be furnished with a copy of the child's DRC. In the case of the SAU group, an Individualized Target Behavior Checklist (ITBC) will be provided ([name] et al., 2010; [name] et al., 2005). The observer will complete this DRC/ITBC each day following the whole-day observation. In addition, the observer will ask teachers in the DRC group for a copy of the day's DRC and ask teachers in the SAU group to complete the same

ITBC. Therefore, we will have the teacher ratings of IEP goal attainment over the three days at baseline and endpoint with built-in procedures to assess inter-rater reliability.

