called/texted the next morning and the child and parent will be asked what contingencies were administered based on school behavior. In addition, teachers will be asked in the SAU and DRC groups about the provision of any school-based rewards. SAU

parents will also be asked whether they received any feedback from the teacher regarding the child's behavior in school that day and in what form (email, DRC, etc.).

In addition, for participants in the DRC group, parents will be asked each day to sign the DRC and record the reward administered, if any. Then, they will return the DRC to the teacher the next morning. This

will help promote home-school communication, and was a procedure used successfully in the Goal 2 project. It is hypothesized that the phone calls to query reward administration will replicate and extend these preliminary findings. Such phone calls have been successfully implemented by our lab on other funded projects (e.g., [name], et al., 2012; NIMH # R34MH078051). The interface between observations of primary outcome and observations of integrity/fidelity during the course of the study is illustrated above. Finally, parents/teachers in both groups will complete a checklist at post-treatment reporting how often they used the components of the DRC intervention (i.e., provided home reward; daily feedback).

Observations for Primary Outcome	Month	Observations for Integrity/Fidelity
SBTR Completed by Observer Blind to Condition (3 total)	January	Integrity/Fidelity Observation(1 total)
N/A	February	Integrity/Fidelity Observation(1 total)
N/A	March	Integrity/Fidelity Observation(1 total)
N/A	April	Integrity/Fidelity Observation(1 total)
SBTR Completed by Observer Blind to Condition (3 total)	May	Integrity/Fidelity Observation(1 total)

10.3 List any instruments or measurement tools used to collect data (e.g. questionnaire, interview guide, validated instrument, data collection form).

Include copies of these documents with your submission.

Response: See description in 10.2 above. In addition, a table of measures and administration schedule is included with the submission.

10.4 Describe any source records that will be used to collect data about subjects (e.g. school records, electronic medical records).

Response: N/A

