Specifically, each outcome score will be regressed on the corresponding pre-test score, a treatment indicator, and four covariates (medication status, grade level, comorbid DBD, and child gender)—the first three of which will be evaluated as potential moderators of treatment in Aim 2. Although the pretest score can be conceived as simply another covariate, it is distinguished here to emphasize the point that its inclusion results in improved statistical power relative to a repeated measures approach for evaluating treatment efficacy (Van Breukelen, 2006). Group differences on adjusted post-test scores (i.e., the significance test of γ_2) will inform the efficacy of using the DRC to enhance academic performance and behavioral outcomes beyond that associated with the routine use of IEP. Measures of primary outcome will be observations of classroom behavior and teacher ratings of academic performance. Measures of secondary outcome will include teacher ratings of symptoms and impairment related to ADHD.

Aim 2. Investigate moderators of treatment outcome.

Aim 2 will be evaluated by extending the ANCOVA model from Aim 1 as follows

$$\gamma_{post}$$

[figure not shown]
$$= \gamma_1 pretest + \gamma_2 DRC + \sum_{j=1}^2 \gamma_j covs \\ + \sum_{k=1}^3 \gamma_k moderator + \gamma_k moderator * DRC + e_i$$

Specifically, Aim 2 will extend the models estimated from Aim 1 by including three additional terms (i.e., the product of each of the three moderators—age group, comorbid DBD, IEP Quality—with the indicator of treatment). Tests of each of these three terms (i.e., $\gamma_{k1}, \gamma_{k2}, \gamma_{k3}$) will inform Aim 2. Each DRC X moderator term that is statistically significant will be probed using simple main effects (i.e., comparisons between DRC and SAU outcomes within each level of the moderator variable) in order to delineate the differential magnitude of treatment on adjusted post-test scores as a function of a given covariate (i.e., primary vs. secondary grade; ADHD only vs. ADHD+DBD; High Quality vs. Low Quality IEP).

Aim 3. Investigate mediators of treatment outcome. Aim 3 will be evaluated using a path analytic approach for testing mediation. The path model will extend the ANCOVA models above by simultaneously

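### The daily DRC/ITBC rating of IEP goals has no obtainable baseline in either arm, and its May score in the DRC arm rests on criteria that can move

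*Combined protocol and SAP*

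**What the plan says.** Section 10.2, Rating of IEP Goals, describes two components.

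- **Daily rating.** Observers and teachers score the child's DRC, or an ITBC in the SAU arm. The section says "we will have the teacher ratings of IEP goal attainment over the three days at baseline and endpoint". The observer completes the sheet "each day following the whole-day observation".
- **End-of-year rating.** Teachers rate improvement on each academic or social IEP goal from 1 to 7, and the items are averaged. This component does not use the DRC and is described the same way for both arms.

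On timing, section 10.1 says "Random assignment will be conducted following the completion of all baseline measures". For the DRC arm, the first consultant visit is where "target behaviors will be identified, operationally defined, and integrated into a DRC". At the second visit "criteria for each target behavior will be modified", and at the monthly meetings that follow "DRC goals will be adjusted as needed". The SAU goal list is also built by the consultant with the teacher, after assignment, and no rule for updating it is given.

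The observation table in section 10.2 gives three SBTR sessions in each of January and May. For each month from January to May it also has one entry reading "Integrity/Fidelity Observation(1 total". The SBTR sessions last thirty minutes; the monthly integrity visit lasts a full school day.

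In section 17.1, Aim 1, "each outcome score will be regressed on the corresponding pre-test score".

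**The concern.** Hypothesis 1 in section 1.2 predicts better IEP goal attainment with the DRC, and section 3.1 lists it among the key outcomes. A comparison of goal attainment needs the same yardstick in both arms, and the Aim 1 model needs a pre-test taken before assignment on that yardstick. The daily component appears to have neither. In the DRC arm the scoring sheet is also the intervention, and the intervention works by revising its own targets. A difference in May, or the lack of one, could then reflect where the criteria stood rather than how the child behaved. Imputation and false-discovery-rate control do not address this.

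**Working it through.** **1. Can the baseline exist?** The order of events, from sections 10.1 and 10.2, is:

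- Baseline observations are made in January, before the intervention.
- Randomization comes after all baseline measures.
- A consultant is assigned after randomization.
- The DRC is first written at that consultant's first visit. The SAU list is made with the consultant, also after assignment.

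So no DRC and no ITBC exists when the baseline is taken. This gap is the same in both arms. If January ratings were instead taken once the sheets existed, they would be post-randomization. In the DRC arm they would also be on treatment, because the teacher starts using the card between visits one and two.

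**2. Is the May yardstick common?** In the DRC arm the teacher supplies that day's DRC, whose criteria may have been changed at visit two and at any monthly meeting. Nothing ties May scoring to the initial criteria, and nothing says whether the SAU list is revised.

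**3. How much can a moved criterion matter?** The plan gives no figure, so this is an illustration. It starts from the section 10.1 example (an average of 10 events, criterion set at 8 or fewer). Two assumptions are added: counts are Poisson, and the score is the chance that a goal is met, P(X ≤ c | mean m).

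| Mean m | Criterion c | P(met) |
|---|---|---|
| 10 | 10 | .583 |
| 10 | 8 | .333 |
| 8 | 10 | .816 |
| 8 | 8 | .593 |
| 6 | 8 | .847 |
| 6 | 5 | .446 |
| 6 | 4 | .285 |

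With behavior unchanged, moving between 10 and 8 shifts the score by .583 − .333 = .250 at mean 10, and by .816 − .593 = .223 at mean 8. Tightening lowers the DRC arm's score and loosening raises it.

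For a child who improves from 10 to 6, a criterion held at 8 takes the score from .333 to .847. Repeating the example's 20% step gives 0.8 × 6 = 4.8. At 5 or fewer the score is .446, a small gain; at 4 or fewer it is .285, no gain. The result depends on the rounding.

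**4. Observation days.** The daily component calls for whole-day observation on three days at each end. The schedule has one whole day per month and three half-hour sessions, so no arrangement in it supplies three whole days.

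**5. The seven-point rating.** It is completed only at the end of the year. It has no corresponding pre-test, so the Aim 1 equation cannot be fitted to it as stated.

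**6. Rank.** Section 2.1 puts a teacher rating of IEP goal attainment in the primary-endpoint paragraph. Section 10.2 introduces the teacher ratings as secondary to the observations. Section 17.1 leaves IEP goals out of its primary list.

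**7. Power without a pre-test.** Two-sided alpha of .05 is assumed, since section 17.2 gives none. First, the plan's figures: n per arm = 2(1 − R²)(1.960 + 0.842)²/d².

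- d = .50, R² = .45: 2 × .55 × 7.85/.25 = 34.5, so 35 per arm and 70 in total (plan: 71).
- d = .40, R² = .45: 2 × .55 × 7.85/.16 = 54.0, so 108 in total (plan: 105).

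Both are close to the plan. With 108 per arm, d = .50 and R² = 0, power is Φ(.50 × √54 − 1.960) = Φ(1.714) = .957. With R² = .45 it is Φ(3.674/√.55 − 1.960) = Φ(2.994) = .999.

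**The case against.** The strongest reply is that the endpoint in section 2.1 is a rating made at the end of the school year. That fits the seven-point rating better than the daily sheet, and the seven-point rating does not use the DRC. A reader might infer that a primary endpoint is scored on different scales in the two arms. The documents do not support that: the scale problem belongs to the daily component, and primary rank is contradicted by sections 10.2 and 17.1.

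A reader might also infer that a real benefit of the DRC is bound to be hidden. That does not follow. Section 10.1 allows adjustment without giving a direction, and the no-gain result in the illustration needs a reset to 4 rather than 5.

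A third tempting inference is that the trial loses its power. It does not for the main effect: .957 at d = .50 even with R² = 0. That is a worst case, since medication, grade, comorbidity and gender stay in the model.

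Other points are fair. The plan is silent on SAU updating rather than stating that there is none, and it says the SAU list is built along the same lines as the DRC. Manuals and a table of measures were submitted separately and may say more. The plan defines no summary score for the daily sheet. The monthly integrity visit yields a rate of target behaviors that does not depend on the criteria, though it is labelled an integrity measure. An improvement rating naturally has no pre-test, so that part is a wording correction.

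None of this removes the core. The order of events rules out the stated baseline, and the May sheet in the DRC arm is the live card.

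**Conclusion.** The point holds for the daily DRC/ITBC component. As written, its baseline cannot be obtained in either arm, and its May score is not on a common footing between arms. Anyone following the text literally would compare arms on different criteria with no valid pre-test, so this is wrong as written and more than missing detail.

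The missing baseline does not itself separate the arms; the possible bias comes from the moving criteria. Its sign is unknown. The shift of 22 to 25 points rests on Poisson counts, on a two-event change in criterion, and on proportion met as the score. It shows that the effect can be large and does not estimate what will happen.

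The seven-point rating is untouched by the moving criteria and needs its analysis model restated. The three statements of rank and the two accounts of the observation days must each be reconciled.

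**What to change.** - **Fixed sheet.** Before randomization, write for every child one list of IEP-based targets with scoring criteria, in the same format in both arms. Teacher and observer score that sheet in January and May. The live DRC is used for treatment only and can be changed as the intervention requires.
- **Score.** Define the summary, for example the proportion of listed targets met, averaged over the scoring days.
- **Model.** Use the January fixed-sheet score as the covariate for the May fixed-sheet score and for the seven-point rating, and say in section 17.1 that the seven-point rating has no pre-test of its own.
- **Endpoint.** State which component is the IEP goal attainment endpoint and give it one rank across sections 2.1, 10.2 and 17.1.
- **Days.** State whether the sheet is scored on the three SBTR days or on the single whole-day visit. Any January scoring must come before assignment.

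The lists and observation visits are already planned, so the main cost is timing. Target listing for all 216 children moves ahead of assignment, while consultants are now allocated afterwards. The IEP copy must also be obtained earlier; for SAU children the updated copy is now collected at the consultant's first meeting. DRC teachers would complete a second short sheet on scoring days. Targets added to a DRC later would not count toward this outcome. A side benefit is that observers would no longer be handed differently named forms by arm, which removes one threat to their blinding.

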In order to control for consultant effects, following random assignment to study group, each child will be randomly assigned a behavioral consultant in a counter-balanced fashion (i.e., therapists will be equally distributed across DRC and SAU groups to control for therapist effects), and will then work with the teacher for the school year. Consultants will be M.A. level school/clinical psychology specialists or special education teachers appointed to the project at each site. We have chosen to use individuals with these credentials to increase the external validity of the intervention as these individuals are likely to be called upon to consult with teachers regarding the behavior of children with ADHD as well as be involved in the assessment of children with ADHD and creation of IEPs in many school districts.

Our approach in this study will be to work directly with parents and teachers rather than through a formal IEP amendment process as we expect this to be consistent with the manner this intervention will eventually be used in practice, if found to be efficacious. We expect that similar to our Goal 2 project, districts will informally implement the DRC procedures through collaboration with the consultant. Should a district wish for a more formal approach, it is actually quite easy to amend the IEP through a parent and/or district request without convening an IEP meeting. As stated in the law [34 CFR 300.324(a)(6)], amendments to a child's IEP after the annual IEP meeting may be made by the entire IEP

team at an IEP meeting or by amending the IEP without another IEP meeting. Thus, “in making changes to a child’s IEP after the annual IEP Team meeting for a school year, the parent of a child with a disability and the public agency may agree not to convene an IEP Team meeting for the purposes of making those changes, and instead may develop a written document to amend or modify the child’s current IEP” [34 CFR 300.324(a)(4)(i)]. Thus, the proposed study procedures will be consistent with regulations mandated under P.L. 108-446 (IDEA, 2004). Of note procedures were implemented with 100% of participants in a prior study across numerous districts without issue ([name] et al., 2010).

10.2 Describe what data will be collected.

NOTE: For studies with multiple data collection points or long-term follow up, consider the addition of a schedule or table in your response.

Response:

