IEP Quality. IEP quality will be assessed using a composite rating by study investigators. Prior to quality ratings, IEPs will be de-identified to remove the participant name and information as well as any information about the school or district. Ratings will evaluate the alignment between needs listed in the IEP with goals/objectives stated in the IEP. This will be one way to determine the quality of the IEP document itself – well-written IEPs should have IEPs with close alignment between academic, behavior, and social/emotional needs and the goals to realize improvement (see appendix C for an outline of the coding sheet to be used in the present study; Pariseau, 2011). We will also track which goals are added by consultants to the DRC that were noted as needs by the teacher, but not listed on the IEP. The occurrence of these issues may indicate that the IEP is outdated, poorly constructed, or not reflective of current behavior. These indicators will comprise an IEP quality score investigated as a moderator. Specifically, the score will be calculated as: (Alignment between needs and goals + additional targets added)/overall alignment). A score of 1 would indicate perfect alignment whereas a score below 1 would indicate discrepancy between needs and goals.

Mediators

Three key components of the DRC intervention that are central to our logic model (see figure in the introduction) will be investigated as mediators of treatment outcome. It is expected that relative to the SAU group, the children in the DRC condition will experience a more positive classroom environment, receive more consistent feedback from teachers, and experience more consistent home-based consequences for school behavior. These three variables will each have a partial mediating effect, and the sum total will fully mediate the effect on treatment outcome.

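### The IEP-quality score adds consultant-set targets as if they improved the IEP, and they are set after randomisation, so the Hypothesis 3 moderator is mis-scored in one component and not purely baseline

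*Combined protocol and SAP*

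**What the plan says.** Section 10.2 (Moderators, IEP Quality) builds the score from two indicators. The first is how well the needs in the IEP match its goals, rated by the investigators from a de-identified copy. The second is a count from the consultation, of goals that the IEP itself lacks: "We will also track which goals are added by consultants to the DRC that were noted as needs by the teacher, but not listed". The section says that such findings "may indicate that the IEP is outdated, poorly constructed, or not reflective of current behavior". It then combines the two: "the score will be calculated as: (Alignment between needs and goals + additional targets added)/overall alignment". The scale is stated next: "A score of 1 would indicate perfect alignment whereas a score below 1 would indicate discrepancy between needs and goals".

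On timing, section 10.1 says: "Random assignment will be conducted following the completion of all baseline measures". It adds that "following random assignment to study group, each child will be randomly assigned a behavioral consultant in a counter-balanced fashion". For the DRC arm, "The first visit will be spent reviewing the IEP" with the teacher, and part of its purpose is to "identify potential target behaviors not currently included on the IEP". Monthly meetings may then change the DRC goals. The SAU arm has no DRC, but its consultant draws up a comparable goal list with the teacher.

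Section 1.2 (Aim 2, Hypothesis 3) predicts a larger DRC effect where IEP quality is low. Section 17.1 tests this as a moderator-by-treatment term and compares high- with low-quality IEPs. The moderators also enter the Aim 3 path model as covariates.

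**The concern.** A feature that the plan reads as evidence of a poor IEP should lower a quality score, or at least not raise it. With the plus sign, a child whose IEP missed several needs can be moved towards the high-quality group by the consultant's own additions. That blurs the contrast on which Hypothesis 3 rests.

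The second problem is timing. A moderator should be fixed before assignment. One component here is recorded after assignment by the staff who deliver the assigned condition. As worded, it counts goals added to the DRC, which only one arm has. If it were counted in that arm alone, the same IEP would score differently by arm, and an interaction test on such a score is hard to interpret.

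**Working it through.** **Notation.** A = documented needs with a matching goal; M = documented needs; T = targets added by the consultant. The printed score is (A + T)/D, where D is what the plan calls overall alignment. D is not defined in the supplied text, and the Appendix C coding sheet was not supplied. Four count readings of D were tried.

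**The plan's own scale first.** With T = 0 and D = M or M + T, the scale works: 6 of 6 gives 6/6 = 1.00 and 3 of 6 gives 3/6 = .50.

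**With added targets:**

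| M, A, T | D = M+T | D = M | D = A+T | D = A |
|---|---|---|---|---|
| 6, 4, 0 | .67 | .67 | 1.00 | 1.00 |
| 6, 3, 0 | .50 | .50 | 1.00 | 1.00 |
| 6, 3, 1 | .57 | .67 | 1.00 | 1.33 |
| 6, 3, 3 | .67 | 1.00 | 1.00 | 2.00 |
| 6, 6, 3 | 1.00 | 1.50 | 1.00 | 1.50 |

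The slopes in T are (M − A)/(M + T)², 1/M, 0 and 1/A. None is negative. D = A and D = A + T can never fall below 1, and D = M can exceed 1. D = M + T fits the stated scale best. Under it, 3 of 6 matched with 3 added targets, (3 + 3)/(6 + 3) = .67, scores the same as 4 of 6 with none.

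**Timing, from section 10.1.** Baseline measures are completed, then the child is randomised, then a consultant is assigned, then targets outside the IEP are sought at the first visit. A and M can be rated from an IEP that predates randomisation; T cannot. No cut-off date for counting T is given.

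**Size.** The documents do not supply the inputs, so these are assumed: 4 to 8 needs per child; 30 to 100% matched; T either 50 or 80% of the documented gaps, or up to 4 needs outside the IEP; and a median split, since section 17.1 gives no cut point. Section 17.2 uses d = .6 and .4 within moderator groups. Applied to low and high quality, the true contrast is .6 − .4 = .20. Recovered contrast in 1,000,000 simulated children (T counted in both arms / in DRC only):

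| T | A/M | D = M+T | D = M |
|---|---|---|---|
| 50% of gaps | .194 | .188 / .186 | .117 / .115 |
| 80% of gaps | .194 | .189 / .183 | .056 / .083 |
| outside IEP, Binomial(4, .5) | .160 | .147 / .144 | .090 / .101 |
| outside IEP, Binomial(4, 1 − coverage) | .165 | .147 / .146 | .064 / .080 |

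True quality was taken as A/M in the first two rows and A/(M + T) in the last two. Against A/M, the loss under M + T runs from .194 − .189 = .005 to .165 − .146 = .019. Under M it runs from .160 − .101 = .059 to .194 − .056 = .138.

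**Type I error.** The null simulations used N = 216, no true moderation, T counted in DRC only, and an assumed quality–outcome slope of .3 SD per SD. Under M + T the error was .050 to .054. Under M it was .082 to .167, falling to .053 to .059 at a slope of .1. With T counted in both arms, or with A/M, it was .043 to .059 throughout.

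**Power.** With residual variance 1 − .45 = .55 (section 17.2), the interaction SE is 4 × √(.55/216) = .202. Power for .20 at two-sided 5% is about 17%, even with a perfect score.

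**The case against.** The strongest reply is that the sign cannot be judged while the denominator is undefined. The plan speaks of ratings, not counts, and the missing coding sheet might settle it. Suppose each need is rated 0 to 2, an added target earns 1, and the denominator is the maximum, 2(M + T). Six fully aligned needs then score 12/12 = 1, and with 3 added targets 15/18 = .83, so added targets do lower the score. This shows that the result depends on the reading. It does not rescue the formula where it matters: six needs with a mean rating of .5 score 3/12 = .25, rising to 6/18 = .33 with 3 added. Poorly aligned IEPs still move up.

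Second, counting in both arms is feasible. Section 10.1 plans an SAU goal list built on the same approach as the DRC, and section 10.2 treats the two lists as parallel elsewhere. That stands, and it would largely remove the arm difference. But the IEP Quality paragraph does not say that the SAU list feeds the score, and the counting would still follow randomisation.

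Third, section 10.2 (Rating of IEP Goals) refers to DRC or checklist ratings on three baseline days. This sits awkwardly with section 10.1, but it does not say that targets are set before randomisation.

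A reader might infer that the Hypothesis 3 test has seriously inflated Type I error. The documents do not support that. It needs denominator M, which breaks the stated scale by exceeding 1, together with DRC-only counting and an assumed strong link between quality and outcome.

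**Conclusion.** The point holds in a limited form. The added-targets component runs against the plan's own account of what it means, and it is recorded after randomisation. The alignment component can be rated from the IEP alone and is not in question on timing, so it would be wrong to call the whole moderator post-randomisation.

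The numerical effect is probably small. Under the best-fitting denominator, about .005 to .02 of a .20 contrast is lost and Type I error stays near nominal. A larger loss of contrast needs denominator M, and Type I inflation needs M with DRC-only counting as well. All sizes rest on assumed counts, matching rates and a median split.

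A reader might also infer that the Aim 3 direct treatment path is biased, because the moderators are covariates there. That is possible if the score depends on arm, but no shift in that path has been quantified. Aim 1 is unaffected, because IEP quality is not among its four covariates. Hypothesis 3 has little power in any case. Severity: minor to should-fix.

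**What to change.** In section 10.2 (IEP Quality), take added targets out of the numerator. Define the primary moderator in both arms as A/M: documented needs with a matching goal divided by all documented needs, rated from the de-identified IEP in force at randomisation. This meets the stated scale exactly and cannot depend on arm. Align the coding sheet, and do not rate the updated IEP copy collected at the SAU meeting unless it is that same version.

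A/M alone drops part of Hypothesis 3, which also concerns incomplete IEPs. An IEP that lists 2 needs, matches both and omits 4 scores 2/2 = 1.00. So add a sensitivity score in which added targets lower quality, A/(M + T); in this example, 2/(2 + 4) = .33. Count T identically in both arms, from the first DRC or SAU goal list, and label the score as post-randomisation.

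The cost is one formula, one coding sheet, one sensitivity analysis and a step to identify the pre-randomisation IEP. A current IEP is already an inclusion criterion (6.1). The intake visit (11.2) and the signed release for school data (16.2) give a route to the document. The N/A answer on source records in section 10.4 would need updating. The downside is that the primary score no longer reflects teacher-noted needs missing from the IEP.
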